11.1 Sample Size

A sample of 410 patients will provide 90% power ($\alpha=0.05$) to detect at least a 0.3 standard deviation (SD) effect size difference between groups, assuming equal group participation. These calculations assume a modest 5% non-compliance and 5% dropout over 18-months of follow-up. The SDMT age-adjusted mean score is estimated at 60 (SD = 13) at baseline (based on healthy control data).³² The effect is based on statin dementia prevention and multiple sclerosis trials, where achieved effect sizes of 0.3-0.4 are clinically meaningful and likely to confer public health benefits.⁴⁵

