6.8.3 Cognitive Assessments

Cognitive assessments will be administered between 9:30am and 12:30pm. Completion of all assessments will take approximately 40 mins.

Name	Format	Purpose	Assessment	Scoring	Normative Data	Test-Retest Reliability
SDMT	Oral	Assesses frontal lobe executive processing.	Requires participants to match numbers to symbols according to a key, containing 9 abstract symbols each paired with a number. Participants verbalise the correct number.	The number of correct symbols within the allowed time, usually 90 seconds ²⁸	There are Australian normative data available for the oral SDMT. ²⁹	The oral SDMT demonstrates excellent test-retest reliability (an intraclass correlation coefficient of 0.89) and only has a small learning effect (Cohen's $d = 0.26$) within a 1-week interval. ³⁰
RAVLT-D	Oral No difference in videoconferencing and face-to-face RAVLT-D have been reported. ³¹	Assesses memory and learning. ³²	Requires participants to learn a 15-item word list over 5 learning trials, followed by a distractor list, and short and long-delayed recall.	Max score = 15	Australian normative data is available in Carstairs, Shores and Myers (2012). ³³	Test-retest reliability of the RAVLT has been reported, with the most reliable measures being the total number of words learned over the learning trials ($r = 0.77$), and performance on the retention trial of the learning list following the presentation and performance of the distractor list ($r = 0.70$). ³²

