11.3 Statistical Analysis

The study follows the ITT principle for analysis. Baseline characteristics will be summarised by treatment group. The primary endpoint of change on the SDMT score will be summarised by means (SD)/medians (interquartile range), with the treatment effect tested by a Wilcoxon test. Continuous endpoints will be summarised by means/medians. The primary analysis will be through logistic regression models adjusted for region, age and sex. A sensitivity analysis will be undertaken with adjustment for baseline imbalances and clinically meaningful confounders. Descriptive statistics will be provided for safety data, where SAEs and treatment discontinuation will be tabulated using standard terminology. Heterogeneity of treatment on the primary endpoint will be assessed in pre-defined subgroups, such as age, time since COVID-19 diagnosis, baseline CRP levels, ethnicity, and prior cardiovascular risk. Analyses will be specified a priori in a full statistical analysis plan. A modelled cost-utility analysis using trial data (HRQoL, captured by EQ-5D-5L; drug costs; and health service utilisation costs, including AEs) will be conducted comparing use of atorvastatin and

standard care. A 5-year time horizon will be undertaken, with analyses conducted in line with accepted Australian standards for use of economic evaluation in decision-making.

12 Outcomes

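### Section 11.1 claims 90% power for 410 participants at 0.3 SD, but its own inputs give 86% with no losses and about 80% after the stated dropout and non-compliance

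*Protocol*

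**What the plan says.** Section 11.1 of the protocol gives the size of the main trial in one sentence: "A sample of 410 patients will provide 90% power ($\alpha=0.05$) to detect at least a 0.3 standard deviation (SD) effect size difference between groups", with equal groups. It then says: "These calculations assume a modest 5% non-compliance and 5% dropout over 18-months of follow-up". The 90% is therefore claimed after losses. The only SD offered is a baseline one: "The SDMT age-adjusted mean score is estimated at 60 (SD = 13) at baseline". The section also gives 0.3 to 0.4 as the range of effect sizes it regards as clinically meaningful. It does not mention sidedness, the test, or a correlation between baseline and 18-month scores.

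Section 11.3 sets the analysis. "The study follows the ITT principle for analysis". The endpoint is a change: "The primary endpoint of change on the SDMT score will be summarised by means" or medians, with a Wilcoxon test for the treatment effect. The same paragraph adds: "The primary analysis will be through logistic regression models adjusted for region, age and sex". Baseline SDMT is not among those covariates. The only reliability figure for the oral SDMT is in section 6.8.3, "an intraclass correlation coefficient of 0.89", and it is for a 1-week interval.

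**The concern.** A two-arm comparison at 0.3 SD with 90% power and two-sided alpha 0.05 needs about 235 evaluable participants per arm. The planned 205 per arm falls short before anyone drops out, yet the section says losses are already covered.

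What is at stake is the stated risk of a false negative. Section 11.1 defends 410 by a 10% chance of missing a 0.3 SD effect, which is the lower end of the range it calls clinically meaningful. If that chance is nearer 20%, a null result would be weaker evidence against a 0.3 SD effect than the protocol leads its ethics reviewers and later readers to expect. The section also leaves unclear which effect the trial is powered for, because 0.3 of the baseline SD and 0.3 of the SD of change can be quite different targets.

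**Working it through.** **Inputs from section 11.1.** N = 410, so n = 205 per arm; effect d = 0.30 SD; alpha = 0.05; dropout 5%; non-compliance 5%; stated power 90%.

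**Assumptions added here.** Two-sided test, since sidedness is not stated. The 0.3 is in SD units of the outcome actually analysed. Under intention to treat, non-compliers stay in and contribute no treatment effect, so d becomes 0.95 × 0.30 = 0.285. Dropout leaves 0.95 × 205 = 194.75 per arm.

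**Formula.** Two-sample t-test, noncentral t with 2n − 2 degrees of freedom and noncentrality d × √(n/2). For 205 per arm and d = 0.30 the noncentrality is 0.30 × √102.5 = 3.04.

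**Attempt to reproduce 90%.**

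| Handling of losses | n per arm | d | Two-sided 0.05 | One-sided 0.05 |
|---|---|---|---|---|
| None | 205 | 0.300 | 85.8% | 91.7% |
| 5% dropout only | 194.75 | 0.300 | 84.0% | 90.5% |
| Both taken off N (10%) | 184.5 | 0.300 | 82.0% | 89.1% |
| 5% dropout, 5% dilution | 194.75 | 0.285 | 80.1% | 87.7% |

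No two-sided row reaches 90%. Applying the usual 0.955 efficiency of the Wilcoxon test under normality lowers the last two-sided figure to about 78%.

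**Sample size needed, two-sided.**
- 90% power, d = 0.30, no losses: 234.46 per arm, total 468.9, or 470 with whole participants in equal arms.
- 90% power, d = 0.285, 5% dropout: 2 × 259.69 / 0.95 = 546.7, about 547.
- 80% power, d = 0.285, 5% dropout: 2 × 194.23 / 0.95 = 408.9, which is close to 410. This suggests, but does not prove, that the calculation was run for 80%.

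**Effect detectable with 90% power.** With 194.75 per arm the detectable difference is 0.3293 SD. Undoing the dilution gives 0.3293 / 0.95 = 0.347, about 0.35 SD.

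**If 0.3 means 0.3 of the baseline SD.** Power then depends on the correlation r between baseline and 18-month SDMT, which the protocol does not give. Assuming the same SD at both times, the standardised effect after dilution is 0.285 / √(2(1 − r)) for an unadjusted change score and 0.285 / √(1 − r²) for an analysis adjusted for baseline SDMT. Two-sided power with both losses:

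| Assumed r | Unadjusted change | Adjusted for baseline |
|---|---|---|
| 0.4 | 73% | 86% |
| 0.5 | 80% | 90% |
| 0.6 | 88% | 94% |
| 0.7 | 95% | 98% |

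Setting each expression equal to 0.3293 gives the correlation needed for 90%: r = 0.50 with baseline adjustment and r = 0.63 (0.625) for unadjusted change. At r = 0.5 the SD of change equals the baseline SD, so an unadjusted change score gains nothing.

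**The case against.** The strongest reply is that two of the inputs above are not the protocol's.

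- **Sidedness.** Section 11.1 does not state it, and the one-sided figures lie on both sides of 90%. But nothing in the protocol declares a one-sided test, and once both stated losses are counted a one-sided test still gives only 89.1% or 87.7%.
- **Which SD.** The only SD in the section is the baseline 13, so 0.3 could mean 0.3 × 13 = 3.9 SDMT points. With a correlation of 0.5 to 0.63, which the 1-week reliability of 0.89 does not make implausible, 90% would be reached. This part stands: true power could be 90% or more, and the document cannot exclude it. It cannot support it either, because a 1-week figure does not settle an 18-month correlation, and at r = 0.4 an unadjusted change score gives only 73%.

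Other points have some force. The covariate list in section 11.3 belongs to a logistic model that does not suit a continuous change, so the absence of baseline SDMT from it is weak evidence about the intended adjustment, and a full analysis plan is promised. The t-test is not the stated test, although the Wilcoxon test gives slightly less power under normality. Full dilution by non-compliers is the harshest of the loss treatments; the mildest that counts both losses as lost participants gives 82.0%, still well short. Finally, the effect detectable with 90% power, about 0.35 SD, lies inside the protocol's own range of 0.3 to 0.4, so 410 remains a defensible number.

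**Conclusion.** The stated power is wrong as written. On a two-sided test at 0.05, with 0.3 in SD units of the analysed outcome, 410 participants give 85.8% power with no losses and 80.1% to 82.0% once both stated losses are counted, against 90% claimed. The chance of missing a 0.3 SD effect is then about 20%, roughly double the 10% implied.

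The 80.1% rests on treating non-compliance as full dilution under intention to treat. The shortfall itself does not, since 90% is missed even with no losses at all. A figure near 90% would need a one-sided test, or a particular SD, analysis and correlation, and the protocol states none of these. The sample size need not change; the claim attached to it should.

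**What to change.** Either of two edits to section 11.1 would settle this.

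1. **Restate the power.** Suggested wording: *410 participants provide about 80% power (two-sided alpha 0.05) for a standardised difference of 0.30 SD of the analysed outcome after 5% dropout and 5% non-compliance; 90% power applies to a difference of about 0.35 SD.*
2. **Keep 90% and give its basis.** Name the analysis and the assumed baseline to 18-month correlation, with the effect set at 0.3 of the baseline SD: about 0.50 with adjustment for baseline SDMT, or about 0.63 for an unadjusted change score. Justify that value with data over a comparable interval, and make the analysis in section 11.3 match.

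In both cases state the sidedness, how dropout and non-compliance enter the calculation, and which SD the 0.3 refers to. Do not convert 0.3 SD to SDMT points using 13 unless 13 is the SD of the analysed outcome.

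The cost is one or two sentences and, under the first option, a less favourable stated power. No extra participants are needed if 410 is kept. Reaching 90% at 0.30 SD without relying on a baseline correlation would take about 547 participants, 137 more than planned (547 − 410).

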11.1.1 Sub-Study Sample Size

For the sub-study, a sample size of 220 (110 per group) is estimated ($\alpha=0.05$) to provide 80% power to detect effect sizes of relative differences of 5.0-6.5 (variance between groups/variance within groups) for the imaging endpoints, assuming a 20% drop out.

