12.2 Key Secondary Outcome

The key secondary outcome is total white matter free water (dMRI) undertaken using data collected in standard procedures using multi-shell diffusion spectral imaging with fibre orientation and compartment modelling. SC members from Monash University have developed a novel computational framework to accurately characterise multi-shell diffusion spectral imaging signals from high b-values whilst retaining the capability of reliably resolving crossing fibres. Three compartments are used to associate brain microstructure to the diffusion signal: an intra-axonal compartment, an extra-axonal compartment, and a third compartment representing the fraction of trapped water molecules with essentially negligible diffusion.

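### Section 11.1.1: the sub-study's effect size, a between/within variance ratio of 5.0-6.5, is inconsistent with its stated 80% power at 110 per group with 20% drop-out

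*Protocol*

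**What the plan says.** Protocol section 11.1.1 is the protocol's only power statement for the imaging endpoints. It says that "a sample size of 220 (110 per group) is estimated" at alpha 0.05 "to provide 80% power to detect effect sizes of relative differences of 5.0-6.5 (variance between groups/variance within groups) for the imaging endpoints". The bracket thus defines that effect size as the between-group variance over the within-group variance. Drop-out is covered by "assuming a 20% drop out".

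The section gives no unit for 5.0-6.5, no mean, SD or CV for any imaging measure, no test and no sidedness. The imaging endpoints include the trial's key secondary outcome (section 12.2): "The key secondary outcome is total white matter free water (dMRI"). By contrast, section 11.1 states the main trial's effect plainly, as 0.3 SD.

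**The concern.** The sentence supplies N, alpha, power, drop-out and an effect size with a verbal definition. For a two-group comparison that is enough to check it as printed, and it does not check.

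Two features suggest that the figure and the bracket do not belong together. First, a relative difference and a variance ratio are different quantities, yet one phrase joins them. Second, for a standardised variance ratio in an unadjusted comparison, one N, one alpha, one power and one drop-out rate give one detectable value. The section gives a range at a single 80%. A range would be natural for percentage differences in means of endpoints with different SDs, but that is not what the bracket says.

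What is at stake is limited. A reader cannot tell what effect the sub-study was sized to detect, so a null result on white matter free water could not be set against the planned effect. The primary outcome, the number scanned and the later inference are not affected.

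**Working it through.** **Inputs from section 11.1.1:** 110 per group, alpha 0.05, power 80%, drop-out 20%, effect 5.0-6.5.

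**Assumptions, not in the document:** two-sided test; unadjusted comparison of two groups (F test on 1 and 174 df, equal to the two-sided t test); variance ratio taken as Cohen's f², so that the standardised difference is d = 2√f².

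**Evaluable numbers.** 110 × 0.8 = 88 per group, 176 in total, residual df 174.

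**What 80% power corresponds to.** The F test on 1 and 174 df reaches 80% at a noncentrality of 7.94. Since noncentrality = d² × 88/2, d = √(7.94/44) = 0.425 SD, and f² = d²/4 = 0.045.

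**Can the plan's 80% be reproduced?**

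| Reading of 5.0-6.5 | Implied quantity | Power, 88 per group, two-sided |
|---|---|---|
| Variance ratio as printed | d = 2√5.0 = 4.47 to 2√6.5 = 5.10 SD | about 100% |
| Variance ratio in percent | f² = 0.050-0.065; d = 0.447-0.510; noncentrality 176 × f² = 8.80-11.44 | 84-92% |
| Noncentrality of the F test | 5.0-6.5 | 60-72% |
| Percentage difference in means | d = difference/CV | 80% only if CV = 5.0/0.425 = 11.8% to 6.5/0.425 = 15.3% |

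- *As printed.* Even 3 per group would give 98-99% power. The stated ratio is more than 100 times the one that corresponds to 80% (5.0/0.045 ≈ 111).
- *In percent.* This keeps the bracket and comes nearest among the variance-ratio readings. Power is above 80% at both ends and differs between them. For 80% it would need 80 and 62 evaluable per group, that is 80/0.8 = 100 and 62/0.8 = 77.5, rounded up to 78, recruited per group, against 110 planned.
- *Noncentrality.* The protocol does not use this term; the reading is included because the definition resembles an F ratio. One-sided it gives 72-81%.
- *Difference in means.* This can give 80% at both ends, but no CV is stated and the bracket describes something else.

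**Sensitivity to drop-out.** With 110 per group analysed, 80% corresponds to f² = 0.036, the percent reading gives 91-96% and the noncentrality reading still gives 60-72%. How drop-out was applied does not explain the mismatch.

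**Sensitivity to sidedness.** One-sided, the percent reading gives 90-96%, and the ratio as printed stays at about 100%.

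**The case against.** A sponsor could answer that a sample sized to provide 80% power meets its aim when power is 80% or more. The ratio as printed and the percent reading both exceed 80%, so nothing falls short. That is right, and it rules out one tempting inference: that the sub-study is underpowered. The documents do not show this. Only the noncentrality reading falls short two-sided, and the protocol never invokes that quantity. The mismatch remains, because a ratio giving about 100% power cannot be the effect that sets N at 80%.

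A reader might also infer that no interpretation whatever yields 80%. That goes too far. A percentage difference in means does so at a CV of about 12-15%. The upper end of the noncentrality reading reaches 81% one-sided. The calculations also assume an unadjusted analysis and one convention for the between-group variance. If that variance is instead the sample variance of the two means (d²/2), a ratio of 0.050-0.065 gives 55-66% unadjusted, and 80% once baseline adjustment with a correlation of about 0.53-0.67 is assumed. Nothing in section 11.1.1 mentions such an adjustment or correlation, so this shows only that the tested readings are not exhaustive.

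A percent sign may simply have been lost. Adding it does not settle the sentence: with the bracket kept, power is 84-92%; with a difference in means intended, the bracket is wrong and the CV is missing.

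Nor can this be left to a statistical analysis plan. The complaint is not missing detail, but that the stated figure, definition and power disagree.

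**Conclusion.** The point holds in a limited form. As printed, the effect size and the 80% power in section 11.1.1 are inconsistent: a variance ratio of 5.0-6.5 implies differences of about 4.5-5.1 SD and about 100% power with 88 evaluable per group, whereas 80% corresponds to a ratio of about 0.045 (about 0.42 SD). These figures assume a two-sided test and an unadjusted two-group comparison. The gap for the printed ratio is too large to depend on sidedness or on how drop-out was handled.

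The document does not reveal whether the figure, the unit or the bracketed definition is in error. It would be wrong to conclude that N = 220 is the wrong size; about 0.42 SD is an ordinary detectable effect for this number. The point should be corrected because it concerns the only stated power for the key secondary outcome, but its reach ends at the sample-size justification.

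**What to change.** Rewrite the one sentence in section 11.1.1 around the planning assumption actually used, giving its unit, its SD or CV and a definition that matches:

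- If a percentage difference in means was meant, write 5.0-6.5%, remove the bracket and state the CV for each endpoint.
- If a variance ratio in percent was meant, add the percent sign, keep the bracket and give the power that it yields (84-92% under the assumptions above).
- If the assumption cannot be recovered, replace it with: *with 88 evaluable per group the sub-study has 80% power (two-sided alpha 0.05, unadjusted) to detect a difference of about 0.42 SD (variance ratio about 0.045)*. Label this as a property of the chosen N and not as the original planning assumption, because it is solved backwards from the sample size.

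The cost is one sentence. The number scanned, the visits and the conduct of the sub-study do not change.

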11.2 Assignment of Intervention

Participants will be registered and randomised via a secure web-based database. The randomisation will be stratified by the following factors: (i) country; (ii) time (<6 vs. ≥ 6 months since acute COVID-19 illness), (iii) age (<60 vs. ≥ 60 years), (iv) Current anosmia that has occurred in relation to COVID-19, and (v) participation in the MRI/biomarker substudy.

11.3 Statistical Analysis

The study follows the ITT principle for analysis. Baseline characteristics will be summarised by treatment group. The primary endpoint of change on the SDMT score will be summarised by means (SD)/medians (interquartile range), with the treatment effect tested by a Wilcoxon test. Continuous endpoints will be summarised by means/medians. The primary analysis will be through logistic regression models adjusted for region, age and sex. A sensitivity analysis will be undertaken with adjustment for baseline imbalances and clinically meaningful confounders. Descriptive statistics will be provided for safety data, where SAEs and treatment discontinuation will be tabulated using standard terminology. Heterogeneity of treatment on the primary endpoint will be assessed in pre-defined subgroups, such as age, time since COVID-19 diagnosis, baseline CRP levels, ethnicity, and prior cardiovascular risk. Analyses will be specified a priori in a full statistical analysis plan. A modelled cost-utility analysis using trial data (HRQoL, captured by EQ-5D-5L; drug costs; and health service utilisation costs, including AEs) will be conducted comparing use of atorvastatin and

standard care. A 5-year time horizon will be undertaken, with analyses conducted in line with accepted Australian standards for use of economic evaluation in decision-making.

12 Outcomes

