12.1 Primary Outcome

The primary outcome is processing speed, assessed by the oral SDMT.

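### The primary analysis is named as logistic regression, but the endpoint is a numeric SDMT change with no binary or ordered response defined, and a Wilcoxon test is given for the same endpoint

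*Protocol*

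**What the plan says.** Protocol section 12.1: "The primary outcome is processing speed, assessed by the oral SDMT". The table in section 6.8.3 gives the score as "The number of correct symbols within the allowed time", usually 90 seconds, so the outcome is numeric.

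Section 11.3 makes change in this score the primary endpoint, to be summarised by mean (SD) or median (interquartile range), "with the treatment effect tested by a Wilcoxon test". No covariates are named for that test. Shortly afterwards the section says: "The primary analysis will be through logistic regression models adjusted for region, age and sex". It adds a sensitivity analysis adjusting for baseline imbalances and confounders, and promises a full SAP.

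Section 11.1 sizes the trial at 410 for 90% power "to detect at least a 0.3 standard deviation (SD) effect size difference between groups", with an SDMT mean of 60 and SD of 13 at baseline.

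Section 11.2: "The randomisation will be stratified by the following factors: (i) country". The other four factors are time since the acute illness, age, current anosmia and participation in the MRI/biomarker sub-study.

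**The concern.** Logistic regression needs a binary or ordered response. The synopsis and sections 11.3 and 12.1 define none for the SDMT, so the model named as primary cannot be fitted without inventing one. A second, different method is attached to the same endpoint, and the text does not say which result decides the trial.

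Neither method gives the quantity a reader needs. Logistic regression yields an odds ratio for an unstated response. The Wilcoxon test, as described, is an unadjusted rank test. Means appear only as summaries, so no adjusted difference in SDMT points is planned.

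The covariate list adds to the mismatch. It omits baseline SDMT and three of the five stratification factors (time since illness, anosmia, sub-study participation), and it says region where the stratifier is country.

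Two things are at stake: power, if the score is dichotomised, and credibility. Treatment is open-label (section 7.2) and the DSMB sees unblinded data including cognitive outcomes (section 13.1), so a cut-off chosen after enrolment begins would invite doubt about how it was chosen.

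**Working it through.** **Inputs from the protocol.** N = 410, equal groups, 0.3 SD, SD 13 (so 0.3 × 13 = 3.9 points), alpha 0.05, 5% dropout and 5% non-compliance (section 11.1).

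**Assumptions.** Two-sided test (sidedness is not stated), normal data, 0.3 SD on the scale analysed, and non-compliance diluting the effect to 0.3 × 0.95 = 0.285 SD. Evaluable per arm: 410 × 0.95 / 2 = 194.75.

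**The plan's own figure.** For a two-sided comparison of means, n per arm = 2 × (1.960 + 1.282)² / 0.3² = 234, or 468 in total before any loss. At 410 with no loss, power is 85.9%. The stated 90% is therefore not reproduced on this reading. It can be reached with an added assumption, such as ANCOVA with a baseline-to-follow-up correlation of 0.5 (90.1% after dilution and dropout). That is a separate point and nothing below relies on it.

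**Formula.** Power ≈ Φ(d × √(nE/2) − 1.96), where E is the efficiency relative to a comparison of means:
- Means: E = 1.
- Wilcoxon: E = 3/π = 0.955. A proportional-odds model should be close to this.
- Cut at proportion p: E = φ(z_p)² / [p(1 − p)], which is 0.637, 0.576 and 0.490 at p = 0.5, 0.3 and 0.2.

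Worked lines at d = 0.3:
- Means: 0.3 × √(194.75/2) = 2.960; Φ(2.960 − 1.96) = 0.841.
- Median split: nE = 194.75 × 0.637 = 124; 0.3 × √(124/2) = 2.362; Φ(2.362 − 1.96) = 0.656.

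| Analysis | 0.300 SD | 0.285 SD |
|---|---|---|
| Comparison of means | 84% | 80% |
| Wilcoxon | 82% | 78% |
| Median split | 66% | 61% |
| 30/70 cut | 61% | 57% |
| 20/80 cut | 54% | 50% |

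A median split at 0.3 SD corresponds to 56.0% against 44.0%, an odds ratio of 1.61.

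**Simulation check at 0.3 SD.** In 20,000 trials the t-test gave 0.84, Wilcoxon 0.82 and a median-split logistic model 0.63, slightly below the formula. A proportional-odds model on 4-point bins gave 0.85 in 331 trials (Monte Carlo SE 0.02).

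**Dependence on the SD.** The SD of 13 is for baseline scores, while the endpoint is change. If the target is 3.9 points, the SD of change is 13 × √(2(1 − r)), where r is the baseline-to-18-month correlation, which the protocol does not give. Without dilution:

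| r (assumed) | Mean change | Wilcoxon | Median split |
|---|---|---|---|
| 0.5 | 84% | 82% | 66% |
| 0.6 | 91% | 90% | 75% |
| 0.7 | 97% | 96% | 86% |

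**Value of adjusting for baseline.** The variance of the ANCOVA estimate relative to unadjusted change is (1 − r²) / [2(1 − r)] = (1 + r)/2. That is 25%, 15% and 5.5% lower at r = 0.5, 0.7 and 0.89. The last value is the one-week intraclass correlation in section 6.8.3, and the 18-month correlation may differ.

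**The case against.** The strongest counter-argument is that a full SAP is promised and could read the sentence as ordinal logistic regression without leaving the protocol's wording, at roughly Wilcoxon power. That stands as a possible reading, and under it little power is lost. It does not remove the defect: the text says neither ordinal nor proportional odds, and it still leaves two methods competing for one endpoint. Only a SAP that moved to a comparison of means would have to depart from the stated model.

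It is also fair that section 11.1 does not say adjusted. A Wilcoxon test is a valid test of a shift in change scores and costs about 2 points of power. Preferring an adjusted mean difference is therefore partly a matter of choice, though it is the natural match to a 0.3 SD target.

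The dichotomised figures are hypothetical because no cut is proposed, and their level depends on r. The loss persists at each r shown, at 11 to 18 points for a median split.

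The covariate complaint is secondary. Covariates are often settled in the SAP, a sensitivity analysis with further adjustment is planned, and region may simply be loose wording for country.

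**Conclusion.** The concern holds. Section 11.3 fixes a model class that does not fit its numeric primary endpoint and sets a different test beside it without ranking the two. This is a stated error, so it cannot be treated as detail deferred to the SAP, and it must be fixed because it leaves the confirmatory test of a phase III trial undefined.

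The contradiction itself rests on no numerical assumption. The size does: with about 195 evaluable per arm, two-sided 0.05 and 0.3 SD on the analysed scale, dichotomising would lower power from 84% to between 54% and 66%. With dilution to 0.285 SD it would fall from 80% to between 50% and 61%. A median split is equivalent to analysing about 124 per arm instead of 195. A proportional-odds reading would avoid most of that loss but is not stated.

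**What to change.** Replace the Wilcoxon and logistic sentences in section 11.3 with one primary analysis: a linear model (ANCOVA) of 18-month SDMT on treatment, adjusted for baseline SDMT and the five stratification factors in section 11.2, plus sex if wanted. Report the adjusted mean difference in SDMT points with 95% CI and p-value.

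Name 18 months explicitly. Sections 11.3 and 12.1 give no time point and the SDMT is also measured at 6 months, but the research question in section 5 concerns 18 months of treatment. Keep the Wilcoxon test as a sensitivity analysis, and delete logistic regression for this endpoint.

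The cost is protocol and SAP wording only. Baseline SDMT and all stratification factors are already collected, so no new data or participants are needed.
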